6.6.7.2.1. Analysis Methods

PGI scores will be analyzed based on the PPE set, with a major focus in participants with RT-PCR-confirmed RSV ARI and LRTD, for the first and second year and the over whole study. Part of the analysis might also be performed for participants with RT-PCR-confirmed hMPV-mediated and influenza-mediated ARI.

For the **PGI-H** collected during an ARI, number of observations, mean, standard error, median, first and third quartile, minimum and maximum of the change from baseline will be tabulated and means with standard errors may be graphically presented per group and time point for the change from baseline.

For the PGI-H, descriptive statistics start and end of each year, as well as the change between the two timepoints will also be calculated for all participants based on the PPE set and for participants with RT-PCR-confirmed RSV ARI, based on the PPE set.

For the **PGI-C** and **PGI-S** scores collected during an ARI, number of observations, mean, standard error, median, first and third quartile, minimum and maximum will be tabulated and means with standard errors may be graphically presented per group and time point.

For the **AUCs** number of observations, median, first and third quartile (q1, q3), minimum and maximum will be calculated and graphically presented with boxplots per group.

The number of participants and days it took them to **return to their usual health** will be summarized and graphically presented with Kaplan Meier curves. Hazard ratios will also be calculated, with a Cox proportional hazard model with time to return to usual health as dependent variable and group as independent variable. Return to usual health will also be summarized by RSV subtype.

In case two or more assessments are reported at the same day then the worst total score will be used. The same applies for the AUC calculations.

In case a participant had multiple RT-PCR confirmed RSV-mediated ARIs or LRTDs during the reported period, then the PGI score or AUC corresponding to the first occurrence of RT-PCR confirmed RSV-mediated ARI or LRTD will be used, respectively.

6.6.7.3. EuroQoL, 5-Dimension, 5-Level Questionnaire

The EQ-5D-5L questionnaire is a standardized instrument for use as a measure of health outcome, primarily designed for self-completion by the participant. It consists of the **EQ-5D-5L descriptive system** and **EQ visual analogue scale** (VAS).

The **AUC for the change from baseline for EQ visual analogue scale** during the ARI will also be calculated.

The descriptive system includes the following dimensions: mobility, self-care, usual activities, pain/discomfort, and anxiety/depression. Each of these 5 dimensions is divided into 5 levels of perceived problems (1=no problem, 2=slight problems, 3=moderate problems, 4=severe problems; 5=extreme problems) (<https://euroqol.org/eq-5d-instruments/>).

Based on the descriptive system the **EQ-5D Valuation index** is calculated. This index summarizes the information of the 5 dimensions of the descriptive system.

- Assign the level code 1, 2, 3, 4 and 5 to each level of the 5 dimensions (see CTP Appendix 9)
- Create a health state for each patient-time point combination. A health state is a combination of 5 level codes: one level code for each dimension. E.g. health state 12543

indicates ‘no problems walking, slight problems washing or dressing myself, unable to do my usual activities, severe pain or discomfort, moderately anxious or depressed’.

- Assign an index value to each health state as defined in Respiratory where EQ-5D health state is converted to a single summary index by applying a formula that essentially attaches weights to each of the levels in each dimension. The algorithm is based on the valuation of EQ-5D health states using the UK TTO (=time tradeoff method) based value set (see Section 7.12).

6.6.7.3.1. Analysis Methods

EQ-5D-5L scores will be analyzed based on the PPE set, with a major focus in participants with RT-PCR-confirmed RSV ARI and LRTD, RT-PCR-confirmed RSV non- LRTD, for the first, second year and over the whole study. Part of the analysis might also be performed for participants with RT-PCR-confirmed hMPV-mediated and influenza-mediated ARI.

The **EQ-5D-5L dimension** responses collected during an ARI, will be summarized descriptively per category, level and day relative to the start of the ARI for the two groups. Stacked bar plots will be used to visualize the EQ-5D-5L dimension.

For the **EQ visual analogue scale** collected during the ARI, number of observations, mean, standard error, median, first and third quartile, minimum and maximum will be tabulated and means with standard errors may be graphically presented per group and time point for the change from baseline.

For the **EQ-5D Valuation index** (See Section 7.12) collected during the ARI, number of observations, mean, standard error, median, first and third quartile, minimum and maximum will be tabulated and means with standard errors may be graphically presented per group and time point for the change from baseline.

For all three measures, descriptive statistics at the start and end of each year as well as the change between the two timepoints will also be calculated for all participants, for participants with RT-PCR-confirmed RSV ARI and for participants with RT-PCR-confirmed RSV LRTD, based on the PPE set.

For the **AUC** number of observations, median, first and third quartile (q1, q3), minimum and maximum will be calculated and graphically presented with boxplots per group.

Additionally, the vaccine efficacy of the first occurrence of RT-PCR-confirmed RSV-mediated LRTD will be calculated, based on the four quartiles of the EQ visual analogue scale collected at baseline for the PPE participants.

In case two or more assessments are reported at the same day then the worst total score will be used. The same applies for the AUC calculations.

For EQ VAS, worse is defined as the lowest number of the ones reported.

6.6.7.4. Days missed from work

The number of days missed from work will be summarized descriptively for participants that normally work with a RT-PCR confirmed RSV ARI, LRTD, non LRTD and Influenza and hMPV-mediated ARI for the first and second year, separately and over the whole study.

6.6.8. Medical Resources Use Questionnaire

Medical resource utilization questionnaire data are collected at ARI Day 29. The questionnaire contains 4 categories of medical resources and each of them has several subcategories (See Attachment 10.11 in CTP).

MRUs scores will be analyzed based on the PPE set, with a major focus on participants with RT-PCR-confirmed RSV-mediated ARI, LRTD, non LRTD and with influenza-mediated ARI and hMPV-mediated ARI for the first and second year separately, and over the whole study.

An emerging use of medical resources is defined as a medical resource visit that was related to an ARI or a complication of an ARI (meaning the ‘Specify number of visits to ARI or its complications’ question in the MRU is equal or larger to one and at least one of the visits should be set as related to an ARI or its complications).

Emerging medical resources utilized will be summarized per category, subcategory and per group. The number of visits and the length of stay will also be summarized per group, as well as the type of contact (home visit, appointment by telephone etc.). For hospital services, length of stay will also be calculated combined for ‘Short term hospital admission’, ‘Hospitalization in general ward’ and ‘Hospitalization in critical Care’.

The proportion of participants in the PPE with emerging medical resource utilizations associated with an RT-PCR-confirmed RSV ARI, RSV-mediated LRTD, influenza-mediated ARIs and hMPV-mediated ARIs will also be summarized with the corresponding VE and will be depicted with forest plots. A similar Exact Poisson regression model as for the primary and secondary endpoints will be used and exact 2-sided 95% CIs for VE (1-relative risk rate) will be calculated. The follow-up time is determined in a similar way as for the primary and secondary endpoints.

Moreover, percentage of participants reporting that their interactions with healthcare providers for study -related visits and procedures affected the number of times they sought medical care outside of the study will be summarized. The type of the effect (increase or decrease of interactions with healthcare providers) will also be summarized.

In case a participant had multiple RT-PCR-confirmed ARIs or LRTDs during the reported period, then the MRU corresponding to the first occurrence of the RT-PCR-confirmed ARIs or LRTDs will be used, respectively.

6.6.9. Approximate ARI Surveillance Compliance

Participants will receive an ARI surveillance question twice per week questioning whether they have experienced any cold or respiratory infection symptoms. The responsiveness of the

participants to this ARI surveillance question will be summarized for both groups for the first year, second year, over the whole study and per risk level.

The approximate number of ARI surveillance questions that each participant is expected to have responded per year will be calculated as follows:

1. First the number of weeks between the start and the end of the year. The start of the first year is defined as the day of vaccination. The end of the first year is defined as the minimum of (the database cut-off date, a day prior to the study Day 365 [or relative day 365, if the Day 365 visit not available but there are ARI surveillance questions available after the relative day 365], date of study discontinuation). The start of the second year is defined as the Month 12 visit (see phases definition in section 6.1.2) and the end of the second year is defined as the minimum of (the database cut-off date, date of study discontinuation/completion).
2. Then:
 - for ARI that are not closed (not censored) by the PI, the number of weeks that the participant experienced an ARI episode between start and end of the year, will be calculated (= duration of the ARIs in weeks, see Section 6.3.1 for the duration definition).
 - For ARI that are closed (censored) by the PI, because the PI assessed that symptoms have permanently worsened, the number of weeks that the participant experienced an ARI episode between start and end of the year, will be calculated (= duration of the ARIs in weeks, see Section 6.3.1 for the duration definition).
 - for ARIs that are closed by the PI because they were not RSV, hMPV or Flu positive and no sputum was collected, then 1.4 weeks (10 days) will be used. Per CTP, these participants will return to ARI surveillance with twice weekly reminders 10 days after the day of onset of this ARI.

Notes:

- ARIs ending prior to the day of vaccination will not be taken into account.
- In case an ARI starts in the first year and ends in the second year, the duration will be split between the two years. The duration from the start of the ARI until the end of the first year will be attributed to the first year, and the duration between the start of the second year and the end of ARI episode will be attributed to the second year. For example, if the ARI started 10 Aug 2022 and ended 23 Aug 2022, and first year ended 14 Aug 2022 and second year started 15 Aug 2022, the overall ARI duration will be 14 days, of which 5 days will be attributed to the first year and 9 days will be attributed to the second year.
- For ARIs that are closed by the PI because they were not RSV, hMPV or Flu positive and no sputum was collected, $\min[(\text{ARI start date} + 10 \text{ days} - 1), \text{last phase date}]$ will be considered as their ‘temporary’ ARI end date,

instead of the end date reported in the CRF. Therefore, in case the ARI starts in the first year and the ‘temporary’ end date falls in the second year, the 10 days duration will be split between the two years, similar to an ARI not closed by the PI. For example, if an ARI closed by the PI started on the 10 Aug 2022, the first year ended 15 Aug 2022 and the second year started 16 Aug 2022, then the duration between the 10 August 2022 and the 15 August 2022 (= 6 days) will be attributed to the first year and the duration between the 16 August 2022 and 19 August 2022 (10 August 2022 + 10 days - 1) (4 days) will be attributed to the second year.

- In case a RSV+ ARI is ongoing at the time of the DB cut off, the date of the DB cut off will be considered as the ‘temporary’ end date of the ARI for the calculation of the ARI duration.
 - In case an ARI episode starts prior to the day of vaccination, only the ARI duration after the vaccination will be used.
3. And finally, the difference of the two (1-2) will be multiplied by 2, since for each week a participant is part of the ARI surveillance journey, we expect to receive 2 questionnaires.

For estimating the percentage of compliance per subjects the number of ARI surveillance questions answered after vaccination, until the end of the year and outside RSV-episodes will be divided by the number obtained in step 3 and will be multiplied by 100.

In case multiple ARI surveillance questions have been answered at the same day, only one will be used.

The approximate number of ARI surveillance questions that each participant is expected to have responded over the whole study will be defined similar as per year, where in the first step the number of weeks between day of vaccination and the minimum of (the database cut-off date, date of study discontinuation, date of completion, end of first year in case of MPD impacting efficacy during the second year).

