 - k. Participants complete the eDiary to respond to the ARI Surveillance Assessment, the RiiQ Symptom Scale and the RiiQ Impact on Daily Activity Scale, the EQ-5D-5L, PGI-H, the PGI-S, the PGI-C, and the Return to Usual Health question once daily (ie, either at home or during the site visit, if applicable). (Note: the PGI-C scale and the Return to Usual Health question will not be completed on ARI Day 1). Participants with a RT-PCR positive for RSV, hMPV, or influenza-mediated ARI will continue filling out the questionnaires until resolution of the ARI episode. Participants with negative RT-PCR results for RSV, hMPV, or influenza will be informed by telephone or telemedicine that they can stop filling out the questionnaires and the site will end the ARI episode and return the participant to ARI surveillance. Participants with a sputum sample taken and participants with at least one nasal swab that cannot be tested at the site with the BioFire Filmarray Respiratory panel will follow the same procedures as participants with a RT-PCR positive for RSV, hMPV, or influenza-mediated ARI. Further details are provided in [Appendix 7: ARI Surveillance Assessment](#).
 - l. All ARIs will be captured in the eCRF for all participants who experience an ARI episode for the duration of the study. All complications (including pneumonia), hospitalizations, concomitant medications, and MRU data associated with medical encounters, and whether they were related to ARIs will be captured in the eCRF for all participants who experience an ARI episode for the duration of the study. ARIs and complications related to ARIs that classify as SAEs will be captured in all participants and reported as SAEs in the eCRF continuously from the time of vaccination until 6 months after vaccination. In addition, ARIs and complications related to ARIs that do not classify as SAEs will be reported as AEs in the eCRF from the time of vaccination through the following 28 days for Safety Subset

- participants only.
- m. For medically-attended RT-PCR positive for RSV, hMPV, or influenza-mediated ARIs, including those resulting in hospitalization, a standard question list will be provided ([Appendix 6: Medically-attended ARI Form](#)) to collect additional information on any other diagnostic tests (eg, chest x-rays, spirometry, pulmonary function tests, etc.) or on any interventions during the clinical course of the ARI.

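### The surveillance-compliance formula takes all ARI time out of the denominator but only RSV-episode answers out of the numerator, so compliance is overstated for participants who answer during a non-RSV ARI

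*SAP*

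**What the plan says.** SAP 6.6.9 builds the expected number of answers in three steps. Step 1 takes the weeks in the year. Step 2 works out the ARI weeks to remove, and covers every kind of episode:

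- "for ARI that are not closed (not censored) by the PI, the number of weeks that the participant experienced an ARI episode", which takes in RSV, hMPV, influenza and sputum-collected episodes at full duration;
- episodes that the investigator closed "because the PI assessed that symptoms have permanently worsened", also at full duration;
- episodes closed as negative for RSV, hMPV and influenza, where, if "no sputum was collected, then 1.4 weeks (10 days) will be used".

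In step 3, "the difference of the two (1-2) will be multiplied by 2". The numerator is the answers given after vaccination, "until the end of the year and outside RSV-episodes will be divided by the number obtained in step 3". Several answers on one day count once. There is no weekly limit and no ceiling at 100%. The whole-study figure is built in the same way. Results are shown for both groups, by year, over the whole study and by risk level.

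**The concern.** The two exclusions do not match. Time in an hMPV, influenza, sputum-collected or negative ARI leaves the denominator, but surveillance answers given in that time remain in the numerator. The error can only push the figure up, and it grows with the number of answers given during non-RSV ARIs.

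It deserves attention because every primary-endpoint case starts from an ARI that the participant reports. SAP 6.6.9 is the SAP's summary of response to routine surveillance. SAP 6.6.10 covers missing questionnaire data and RiiQ completion within episodes already detected, which is a different question. If strata differ in the frequency of non-RSV ARIs, the one with more of them will look somewhat more compliant than it was.

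**Working it through.** **The plan's own figures.** The SAP states no compliance percentage, but its two day-count examples reproduce with an inclusive count. 10 to 23 August is 14 days, split 5 + 9. 10 to 19 August is 10 days, split 6 + 4. Ten days is 10/7 = 1.43 weeks, given as 1.4, which is rounding only.

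**Do answers fall inside non-RSV episodes?**

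- Protocol Appendix 7: a yes to the surveillance question opens the ARI assessment, and the participant then gives the date on which symptoms began. That answer normally falls on or after ARI onset, hence inside the episode.
- Protocol 8.1: the question can be answered at any time, and twice a week is a minimum.
- Protocol 1.3.2 footnote k, on the once-daily episode diary: "Participants complete the eDiary to respond to the ARI Surveillance Assessment", followed by the RiiQ and the other scales.
- Against daily answering: the Synopsis footnote listing the daily episode questionnaires and the lists in Protocol 8.1 omit the surveillance question, and several places describe a return to surveillance after the episode.

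One answer per episode is therefore well supported. Daily answering is possible but not settled.

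**Formula.** Let D = 2 × (52 − ARI weeks removed), c = the share of expected answers given outside ARIs, and a = the answers given inside non-RSV ARIs. As written, compliance = 100 × (cD + a)/D = 100 × (c + a/D). The overstatement is 100 × a/D points, whatever the value of c. The 52-week year, c = 90%, the numbers of ARIs and answers, and the 3-week influenza/hMPV duration are illustrative assumptions.

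| Non-RSV ARIs in the year | D | a | Overstatement (points) | Reported if c = 90% |
|---|---|---|---|---|
| None, or RSV ARIs only | – | 0 | 0 | 90.0% |
| One negative, opening answer only | 2 × 50.6 = 101.2 | 1 | 1.0 | 91.0% |
| One negative, 3 answers | 101.2 | 3 | 3.0 | 93.0% |
| One negative, daily for 10 days | 101.2 | 10 | 9.9 | 99.9% |
| Three negative, opening answers only | 2 × 47.8 = 95.6 | 3 | 3.1 | 93.1% |
| One 3-week influenza/hMPV, opening answer only | 2 × 49 = 98.0 | 1 | 1.0 | 91.0% |
| One 3-week influenza/hMPV, daily | 98.0 | 21 | 21.4 | 111.4% |

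Each answer is worth about 1 point (1/101.2 to 1/95.6). For a negative ARI, ten answers is a ceiling. The site visit is on ARI Day 3-5 and swab testing follows within 48 hours, so the daily diary would usually stop by about Day 5 + 2 = Day 7. Seven answers give 7/101.2 = 6.9 points.

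With the numerator restricted to answers outside all ARIs, a = 0 and every row returns 90.0%.

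**The case against.** The strongest counter-argument concerns the mechanism. A reader might take footnote k to mean that participants answer the surveillance question every day of an episode, and so infer inflation of many points. The documents do not establish this. What is counted is surveillance answers, not diary entries, and the other descriptions of the episode diary leave the surveillance question out. If it is suspended during an episode, only the opening answer is left, and with no answer inside the episode there is no bias. This objection stands against any fixed large figure. It does not remove the mismatch, because the opening answer normally lies inside the episode.

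The wording may also be a slip for ARI episodes, and the section calls itself approximate. Both are fair, but a programmer following the text would build the filter as written.

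Finally, SAP 6.11 curtails the final analysis after early termination, and surveillance compliance is not among the items listed. The point therefore matters only where this table is actually produced.

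**Conclusion.** As written, the rule overstates compliance for any participant with a surveillance answer inside a non-RSV ARI. It is consistent for participants with no ARI or only RSV ARIs. The size is about 1 percentage point per such answer over a year: about 1 point per ARI if only the opening answer falls inside, and up to about 10 points for a 10-day deduction if the question is answered daily. Longer influenza or hMPV episodes scale at the same rate per answer. The documents give neither the number of answers during episodes nor the frequency of non-RSV ARIs, so no group-level figure can be stated. Participants without such an ARI dilute the effect.

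Three stronger inferences are not supported:

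- **That a value above 100% is the mark of this error.** The mismatch can produce one, but so can ordinary use of a question that is always open: three answers a week with no ARI gives 3 × 52 / (2 × 52) = 156/104 = 150%.
- **That the comparison between arms is distorted.** Allocation is randomised and blinded, the error arises only in non-RSV ARIs, and nothing in the documents shows that their frequency or the answering habit differs by arm.
- **That the efficacy result is affected.** The summary is descriptive and enters no endpoint, analysis set, follow-up time, alpha or success rule.

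This is a minor correction, but a clear one.

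**What to change.** In the numerator sentence of SAP 6.6.9, replace *outside RSV-episodes* with *outside the ARI periods subtracted in step 2*. Use the same start, end and temporary end dates as that step, including the 10-day end date for negative ARIs and the database cut-off date for ongoing RSV episodes. Apply the same rule to the whole-study version.

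The alternative of subtracting only RSV time from the denominator would not restore the routine rate. With c = 90% and one negative ARI it gives (91.08 + 1)/104 = 88.5% with the opening answer only, and (91.08 + 10)/104 = 97.2% with daily answers.

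The cost is one phrase and one programming filter, with no new data. If the table has already been produced, rerun it or add a footnote stating the rule used.

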6.6.10. ARI Missing Data

The reason and number of days with ARI missing data will be analyzed based on the PPE set, with a major focus on any RT-PCR confirmed RSV, Influenza and hMPV-mediated ARI for the first year, second year, over the whole study and per risk level.

During the day of vaccination, at month 12, month 24 and during the ARI episodes the site will collect the reason for missingness in case there are missing ePro assessments. These reasons will be tabulated for all participants per assessment and per group, per timepoint. The reason of missingness for the different assessments will similarly be tabulated, per year. More than one reason might be reported during one ARI episode.

Moreover, based on the RiiQ assessments descriptive statistics of the number of days with missing assessments during the first 7 days of an ARI episode, the first 14 days of an ARI episode and during the full ARI episode will be summarized per group and depicted with stacked bar plots.

The start of the ARI (CESTDTC) will be used for this calculation.

Finally, the percentage of compliance based on the RiiQ assessments will be calculated as follows:

- Compliance over the whole episode is defined as: $\text{Nr of days with RiiQ assessments} / \text{duration of episode} \times 100$
- Compliance during the first seven days is defined as: $\text{Nr of days with RiiQ assessments between day 1 and day 7} / \min(\text{duration episode}, 7 \text{ days}) \times 100$
- Compliance during the first 14 days is defined as: $\text{Nr of days with RiiQ assessments between day 1 and day 14} / \min(\text{duration episode}, 14 \text{ days}) \times 100$

For example: For a subject with an ARI episode duration of 21 days with missing RiiQ assessment on day 4, 8 and 19, the compliance over the whole episode is $18/21 \times 100$, the compliance during the 1st 7 days is $6/7 \times 100$, the compliance over the 1st 14 days is $12/14 \times 100$.

